6.3.1.3. Missing EFP Onset Date

Missing EFP onset days will be calculated as the first day of the month and missing onset month will be recorded as January. If the EFP onset date is indicated as completely unknown but starting less than 5 years ago, the EFP onset date will be calculated as the informed consent date minus 5 years. If the EFP onset date is indicated as completely unknown but starting more than 5 years ago, the EFP onset date will not be imputed. Missing EFP medication/treatment end days will be imputed with the last day of the month and missing end months will be imputed with December, except if the end year is equal to the date of injection year and then the EFP medication/treatment end date will be imputed with the first injection date.

6.4. Interim Analyses

No interim analysis is planned for this study.

6.5. Treatment Groups

A single dose of CCH will be administered in this study. Subjects will be summarized overall as “CCH 3.36 mg.”

7. STATISTICAL ANALYSES

7.1. Subject Disposition

The number of subjects included in each study population will be summarized. Subjects excluded from the Safety, PK, or Cellulite Severity Populations will be listed.

The number and percent of subjects screened, completed, and discontinued during the study, as well as the reason for discontinuation will be summarized. Subject time in the study will be summarized descriptively (See [Table 11](#) for computation of time in the study). A listing of all subjects who discontinued the study will be provided.

7.2. Protocol Deviation

Protocol deviations will not be summarized. A listing of all protocol deviations will be presented.

7.3. Demographics and Baseline Characteristics

Demographics and baseline characteristics will be summarized using the Safety Population. Age, height (at screening), body weight (at screening) and body mass index (BMI) in kg/m² will be summarized as continuous variables using descriptive statistics.

Gender, race and ethnicity will be summarized as categorical variables using frequency counts and percentages.

Skin category based on Fitzpatrick scale rating will be summarized using frequency count and percentages.

History of tobacco and alcohol use will be summarized using frequency count and percent as:

- Alcohol use (Never, Current or Former)
- Tobacco use (Never, Current or Former)

All demographic and baseline characteristics will be presented in subject listings.

7.4. Medical and Surgical History

Medical history will be coded using the MedDRA dictionary (version defined in the DMP). A subject listing of medical history data will be provided.

7.5. EFP History

EFP history will be summarized using counts and percentages using the Safety Population, and will include:

- Family history of cellulite (Yes/No)
- Age (years) at EFP symptom onset (summarized descriptively)
- Prior treatments for EFP including liposuction, laser, massage, radiofrequency, drug, mesotherapy, cream, other, or none. Subjects can report more than 1 prior EFP treatment.
- Number of prior EFP treatments (0, 1, 2, or ≥ 3)
- Time (years) since most recent EFP treatment (summarized descriptively)

Refer to [Table 11](#) for computation of “age at EFP onset” and “time since last EFP treatment”. EFP history will be listed.

7.6. Concomitant Medications and Procedures

Prior and concomitant medications will be summarized using frequency counts and percentages by active ingredient within each ATC, with ATC and active ingredients ordered alphabetically. Multiple use of the same medication by a subject will be counted only once.

A subject listing of prior and concomitant medications and procedures will be presented. A separate listing of prior and concomitant medications and procedures for EFP/Cellulite will also be presented.

7.7. Cellulite Severity Evaluations

The Cellulite Severity Population will be used for all the analyses.

The CR-PCSS ratings will be summarized at baseline. Change from baseline in severity will be summarized at EOS by quadrant using counts and percentages for each severity rating and with mean and SD. A shift table of CR-PCSS ratings at Baseline and EOS will be presented using counts and percentages.

The investigator CR-PCSS responder classification for 2-point responders and 1-point responders will be summarized using count and percentages at EOS by each quadrant.

A listing of cellulite severity ratings will be presented. If cellulite severity was not rated, the reason for the lack of assessment will be presented.

7.8. Pharmacokinetic Analyses

7.8.1. Plasma Concentration

Plasma concentrations of AUX-I and AUX-II will be summarized using descriptive statistics at each nominal sample time point. The number of samples above the lower limit of quantification and BLQ will be summarized. The handling of missing and BLQ data is described in section [6.3](#).

The listing will also include the actual time of the sample collection from the time of last injection.

Figures of mean (\pm SD) AUX-I and AUX-II plasma concentrations by time using nominal time will be presented on a linear and semi-logarithmic scale. Individual AUX-I and AUX-II plasma concentration actual time plots will also be presented using linear and semi-logarithmic scales.

The PK Population will be used for summary and plots.

7.8.2. Pharmacokinetic Parameters

AUC_{0-t} , AUC_{0-inf} , C_{max} and T_{max} will be summarized using descriptive statistics for the PK Population. In addition, the geometric mean and coefficient of variation (CV) will be calculated and presented for AUC_{0-t} , AUC_{0-inf} , and C_{max} . Geometric means and CV will be calculated for the log transformed parameters. The CV will be calculated as:

$$CV (\%) = \text{SQRT}[\exp(\text{SD}^2) - 1] * 100$$

The handling of missing and BLQ data is described in section [6.3](#). Individual AUX-I and AUX-II PK parameters will be listed.

7.9. Safety Analyses

Safety data will be summarized using the Safety Population.

7.9.1. Study Drug Exposure

The number of injections of study drug given on Day 1, will be summarized by counts and percentages for each quadrant:

- Subjects who received 12 injections per quadrant
- Subjects who received less than 12 injections per quadrant along with reason

Following will be summarized by each quadrant using descriptive statistics:

- number of injections given
- number of dimples treated
- average number of injections per dimple

A subject listing of overall exposure, and injection status will be provided along with the reasons for receiving less than 48 injections (12 injections per quadrant).

7.9.2. Adverse Events

All AE summary tables will include only TEAEs, unless otherwise specified.

AEs will be summarized by SOC and PT. A subject will only be counted once per SOC and PT.

For AEs by severity grade (mild, moderate, severe), if a subject has multiple events occurring in the same SOC or same PT, then the event with the maximum intensity (ie, severe) will be counted.

For AEs by relationship to study drug, if a subject has multiple events occurring in the same SOC or same PT, the event with the highest association (ie, related) to study drug will be summarized.

AEs will be presented in decreasing order of the incidences at SOC level and within each SOC, in decreasing order of the incidences at the PT level.

An overall summary of AE and AE related to study drug will be presented and will include:

- Total number of TEAEs reported
- Total number of TEAEs reported by severity
- Total number of AEs of special interest
- Subjects with any TEAE
- Subjects with any AE of special interest
- Subjects with any serious TEAE
- Subjects with any severe TEAE
- Subjects with no severe TEAEs, but at least one moderate TEAE
- Subjects with no severe TEAEs, but at least one mild TEAE
- Subjects with any TEAEs leading to drug interruption/withdrawn
- Subjects with any TEAEs leading to study discontinuation
- Subjects with any TEAEs resulting in death

Statistical Analysis Plan (SAP) Module 1 – Study EN3835-103

The following summary tables will be presented by SOC and PT:

- All TEAEs
- TEAEs by Severity
- All non-study drug related TEAEs
- All study drug related TEAEs
- Study drug related TEAEs by severity
- Serious TEAEs
- Duration of study drug related TEAEs (<14 days, 14 – 21 days and >21 days)
- AEs of Special Interest

Serious and most common non-serious TEAE by order of frequency (Most frequent, 2nd most frequent and 3rd most frequent) will be summarized by PT. Most common non-serious AEs are any PT that at least 5% of the subjects reported at least once.

The following listings will be presented by patient:

- All AEs
- Serious AEs
- AEs of special interest
- AEs resulting in drug interruption/withdrawn
- AEs resulting in study discontinuation
- AEs resulting in deaths

Refer to [Table 11](#) for computation of duration of AE.

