14.4. Intensity Assessment

The intensity (or severity) of AEs is characterized as mild, moderate, or severe:

- **Mild** AEs are usually transient, requiring no special treatment, and do not interfere with the subject's daily activities.
- **Moderate** AEs introduce a low level of inconvenience or concern to the subject and may interfere with daily activities, but are usually ameliorated by simple therapeutic measures.
- **Severe** AEs interrupt a subject's usual daily activity and typically require systemic drug therapy or other treatment.

When the intensity category of an AE changes, the greatest intensity during that continuous episode should be recorded.

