16.6.4. Adverse Events

The Medical Dictionary for Regulatory Activities (MedDRA) will be used to code AEs. The version used in this study will be stated in the Data Management Plan.

An AE (classified by preferred term) that started during the treatment period will be considered a TEAE if it was not present prior to the first dose of study drug, or was present prior to the first dose of study drug but increased in intensity during the treatment period. If more than 1 AE is reported prior to the first dose of study drug and coded to the same preferred term, then the AE with the greatest intensity will be used as the benchmark for comparison to the AEs occurring during the treatment period which were also coded to that preferred term. Any AE present prior to the first dose of study drug that increases in intensity during the treatment period will be re-entered with a new start date of the date of increased intensity.

Descriptive statistics (the number and percentage) for subjects reporting TEAEs will be tabulated by system organ class and preferred term; by system organ class, preferred term, and severity; and by system organ class, preferred term, and relationship to study drug. If more than 1 AE is coded to the same preferred term for the same subject, the subject will be counted only once for

that preferred term using the most severe and most related occurrence for the summarization by severity and by relationship to the study drug.

Listings will be presented for subjects with SAEs, subjects with AEs leading to discontinuation, and subjects who die (if any).

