3.1. Determination of Sample Size

A sample size of 12 subjects enrolled was chosen empirically based on the pragmatic criteria and published data of previous studies in order to have at least 10 subjects complete the study.

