6.3. Handling of Missing Data

Subjects who discontinue the study prior to or after the initiation of the study drug will not be replaced and available data for these subjects until the point of discontinuation will be summarized. Any missing baseline assessments will not be imputed.

For categorical variables with missing values, a category documenting the frequency of missing values will be displayed in the summary tables.

Subjects who discontinue early will be requested to complete all Day 22 procedures and assessments at an early termination visit.

There will be no imputation of missing values for safety data, however missing relationship between AE and study drug will be considered as related to study drug following the WOCF rule. Missing severity of an AE will be summarized as a severe AE.

Samples with a positive titer value for both anti-AUX-I and anti-AUX-II antibodies will undergo a log transformation for analyses. Samples with titer level less than 1 will be assigned or imputed as a log transformed titer of zero (0) for analyses.

All plasma concentration values below the limit of quantification (BLQ) will be set to zero (0) in calculation of summary statistics. If the plasma concentration levels are BLQ for all subjects at a time point, then Not Calculable (NC) will be reported in the summary table. Any missing samples will be reported as 'Missing' and treated as missing for PK parameter and plasma concentration summary calculations. C_{max} , AUC_{0-t} , AUC_{0-inf} will be imputed as 0 and Terminal rate constant and T_{max} will be imputed as 'missing' when all plasma concentrations are below lower limit of quantifications.

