11. TABLES, LISTINGS, AND GRAPH SHELLS

The layouts of the summary tables, subject listings, and graphs are presented in SAP Module 2. These layouts incorporate all the appropriate table titles, table numbers, and footnotes.

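### The mild row of the SAP 7.9.2 adverse event overview does not exclude moderate events, so a subject with mild and moderate but no severe TEAEs is counted in two severity rows

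*SAP*

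**What the plan says.** SAP 7.9.2 specifies an overall summary for all TEAEs and for drug-related TEAEs. Among its subject-level rows are a count of subjects with any TEAE and three rows by severity. The first counts subjects with any severe TEAE. The second is "Subjects with no severe TEAEs, but at least one moderate TEAE". The third is "Subjects with no severe TEAEs, but at least one mild TEAE".

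Three other provisions deal with a subject who has more than one grade:

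- SAP 7.9.2, for the tables by severity: where a subject has "multiple events occurring in the same SOC or same PT, then the event with the maximum intensity (ie, severe) will be counted".
- Protocol 16.6.4, which counts a subject once for "that preferred term using the most severe and most related occurrence for the summarization by severity".
- Protocol 14.4, for an event whose intensity changes: "the greatest intensity during that continuous episode should be recorded".

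SAP 6.3 adds that "Missing severity of an AE will be summarized as a severe AE", so every TEAE carries one of three grades in the analysis. On table layouts, SAP 11 says "The layouts of the summary tables, subject listings, and graphs are presented in SAP Module 2". Module 2 is not among the documents reviewed.

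**The concern.** The second row has the form of a step in a worst-severity breakdown: remove subjects with a severe event, then count those with a moderate one. The natural third step removes subjects with a severe or moderate event and counts those left with mild events only. The SAP repeats the exclusion of severe events and omits moderate ones.

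A subject with, say, mild bruising and moderate pain therefore meets both lower definitions. Anyone reading the third row as the number whose worst event was mild would get too large a number, and the three rows could add to more than the number with any TEAE. Two programmers could also produce different counts, one following the literal text and the other the apparent hierarchy. Safety is a primary objective and the sample is small, so a single subject visibly moves a percentage.

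**Working it through.** **Inputs.** The three row definitions and the any-TEAE row come from SAP 7.9.2. The three grades come from SAP 4.6.1. Missing severity is set to severe under SAP 4.6.1 and 6.3, so no TEAE is ungraded. On sample size, SAP 3.1 states "A sample size of 12 subjects enrolled was chosen empirically", and SAP 3 says these subjects will receive the dose. The plan gives no figure of its own to reproduce here.

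**Step 1: do the maximum-intensity rules remove the overlap?** No. The SAP rule applies within an SOC or preferred term, and the protocol 16.6.4 rule within a preferred term. Neither is stated for the subject-level overview, and neither would remove a mild event in one SOC when the moderate event is in another. The protocol 14.4 rule fixes one grade per continuous episode, so two separate events can still carry different grades.

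**Step 2: enumerate the patterns.** Code each grade as 1 if the subject has at least one TEAE of that grade. The rows are then:

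- severe row = severe
- moderate row = not severe and moderate
- mild row as written = not severe and mild
- mild row as corrected = not severe and not moderate and mild

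| Mild | Moderate | Severe | Severe row | Moderate row | Mild row, as written | Sum, as written | Mild row, corrected | Sum, corrected |
|---|---|---|---|---|---|---|---|---|
| 1 | 0 | 0 | 0 | 0 | 1 | 1 | 1 | 1 |
| 0 | 1 | 0 | 0 | 1 | 0 | 1 | 0 | 1 |
| 0 | 0 | 1 | 1 | 0 | 0 | 1 | 0 | 1 |
| 1 | 0 | 1 | 1 | 0 | 0 | 1 | 0 | 1 |
| 0 | 1 | 1 | 1 | 0 | 0 | 1 | 0 | 1 |
| 1 | 1 | 1 | 1 | 0 | 0 | 1 | 0 | 1 |
| **1** | **1** | **0** | **0** | **1** | **1** | **2** | **0** | **1** |

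As written, six of the seven patterns are counted once. The pattern of mild and moderate without severe is counted twice. With the corrected row, all seven are counted once.

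**Step 3: size.** Let k be the number of subjects with the double-counted pattern. Then:

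- severe + moderate + mild rows = any TEAE + k
- printed mild row = mild-only subjects + k

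With 12 subjects in the safety population, each unit of k is 1/12 = 8.3 percentage points. The documents give no severity split, so k is unknown; it can lie anywhere from 0 to 12.

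**Step 4: is the pattern plausible?** Protocol 8.3 reports treatment-related injection site bruising in 75.1% and pain in 59.3% of 189 treated women in the Phase 2b study. At least 75.1 + 59.3 − 100 = 34.4% must have had both, so several distinct events in one subject are common with this product. Protocol 8.1.1 describes most TEAEs as mild or moderate. The Phase 2b study treated one quadrant over three visits, whereas this study treats four in one session, so these figures show plausibility and do not estimate k.

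**The case against.** The SAP nowhere says that the three rows are mutually exclusive or that they sum to the any-TEAE count. Each label states its own condition in full, and a reader who takes the third row literally gets a correct count of what it describes. That much stands: the intended hierarchy is inferred from the wording of the moderate row. The inference is a strong one, though. If overlapping counts were wanted, the exclusion of severe events would serve no evident purpose. As written, the third row gives neither the number with any mild event nor the number whose worst event was mild.

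The printed table cannot be seen either. The Module 2 shell may already carry exclusive wording or a footnote, so the point covers the Module 1 text only.

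The practical harm is also limited. The study is single-arm and descriptive, and no test or decision threshold in the supplied documents uses this row. The severe and moderate rows, event counts by severity, SOC and preferred-term tables, and listings are unaffected. Because missing severity is treated as severe, the mild-only count can be recovered as any TEAE minus severe minus moderate. All of this is right and keeps the point small. But recovery by subtraction helps only a reader who has noticed the problem.

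Finally, the 8.3 points assume that all 12 planned subjects are dosed. With fewer, each affected subject weighs slightly more.

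**Conclusion.** The concern holds on the text of SAP Module 1. The mild row omits the exclusion of moderate events, no other rule in the SAP or protocol supplies it, and a subject with mild and moderate TEAEs but no severe TEAE is counted in both lower rows. Each such subject raises the mild row by one (8.3 percentage points if 12 are dosed) and makes the severity rows exceed the any-TEAE count by one. The total effect depends on k, which the documents do not give and which may be zero.

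Calling the mild row overstated rests on reading the three rows as a worst-severity breakdown, which the moderate row implies but the SAP does not state. The matter is minor, but it affects a printed subject count and should be corrected.

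**What to change.** In SAP 7.9.2, reword the third severity row so that it counts subjects who have at least one mild TEAE and neither a severe nor a moderate one. Apply this to both the all-TEAE and the drug-related overview, and check that the Module 2 shell uses the same definition. The three rows will then sum to the number of subjects with any TEAE, or with any drug-related TEAE, which gives the programmer a simple check.

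The cost is one phrase in the SAP and a look at the shell. No new data or analysis is needed.

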7.9.3. Clinical Laboratory

Laboratory results (hematology and biochemistry) will be summarized using descriptive statistics for observed and change from baseline values at baseline and Day 22.

The PCI laboratory values will be summarized by counts and percentages. Refer to [Table 8](#) for PCI criteria.

A subject listing (including urinalysis results) will be presented for all laboratory parameters.

Serum and urine pregnancy test results, urine drug screen results and alcohol breath test results will be listed by subject.

7.9.4. Vital Signs

Vital signs (systolic and diastolic blood pressure, pulse rate, respiratory rate, body temperature, and body weight) will be summarized using descriptive statistics for observed and change from baseline values for all assessments visits. The PCI vital signs values will be summarized by counts and percentages. Refer to [Table 9](#) for PCI criteria.

A listing of vital signs by subject will be presented.

7.9.5. 12-Lead ECG

The investigator interpretation of ECG results (normal, abnormal not clinically significant or abnormal clinically significant) will be summarized using frequency counts and percentages.

A listing of investigator interpretation of ECG results by subject will be presented.

7.9.6. Physical Examination

Physical examination (by body system) screening results by subject will be presented.

7.9.7. Immunogenicity

The immunogenicity profiling will be performed only if clinical findings and/or PK results warrant immunogenicity profiling.

The immunogenicity analysis of binding and neutralizing anti-AUX-I and anti-AUX-II antibodies will summarize the number of subjects with an immunogenicity sample, the percentage of subjects with a positive sample, and a descriptive summary of the average titer level of the positive samples at Day 1 and EOS. The titer levels will be logarithmically transformed prior to being summarized.

A listing of immunogenicity results by subject will be provided.

8. CHANGE FROM PROTOCOL

This SAP is prepared based on the study protocol dated September 07, 2018 and there are no planned changes either in the conduct of the study or planned analysis at the time of preparing this SAP.

[Table 12](#) lists any significant changes in the SAP from what is proposed in the protocol.

Table 12: Changes from Protocol

Text in Protocol	Change in SAP	Justification

9. REVISION HISTORY

The non-editorial changes made to any of the modules of this SAP will be recorded in Table 13.

Table 13: Revision History

Version	Date	Revision Author	Comments
1.0	27-Oct-2018		Original

11. TABLES, LISTINGS, AND GRAPH SHELLS

The layouts of the summary tables, subject listings, and graphs are presented in SAP Module 2. These layouts incorporate all the appropriate table titles, table numbers, and footnotes.
